Subjects will be allowed to have snacks between the hours of 2100 on day 1 and 0600 hours on day 2 of their CRC study, or at any time for CGM or Reference Glucose Values less than 70 mg/dL or for symptoms of neuroglycopenia. Subjects will preselect their breakfast, lunch, and dinner meal choices from the CRC menu prior to the study. These meals will be unannounced to the FUSION system. Once the closed loop glucose control period has ended after 24 hours of glucose control, the control software will be stopped, and the subject will be disconnected from all intravenous infusions.

If the subjects are removed from the study due to the occurrence of a severe hypoglycemic event (< 54 mg/dL), the subjects will have their glucose values measured with a Reference Glucose Analyzer (e.g., Nova StatStrip Hospital Glucose Meter System) every 10 minutes, until their Reference Glucose Values are greater than 70 mg/dL. They will then have additional Reference Glucose Values drawn every 30 minutes, until they have consistent Reference Glucose Values in the range of 80-250 mg/dL for a period of at least two hours. See *Recovery Period* (Pages 107-108) for details with regards to subcutaneous insulin doses to be received prior to discharge from the Clinical Research Center.

The insulin and dextrose 50 mL medication syringes may not be used for more than 24 hours. Although the study should be terminated after a period of 24 hours (e.g., may not go longer than 24 hours), if for any reason the study period is longer than 24 hours (e.g., on orders from the principal investigator), the insulin and dextrose medication syringes must be exchanged for new medication syringes. To be clear, the insulin and dextrose medication syringes may not be used for a period of time exceeding 24 hours.

8.1.1.6 VISIT 3, TIME 29 TO 32 HOURS (OBSERVATION AFTER CLOSED LOOP GLUCOSE CONTROL SESSION)

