| 14. | 
Termination Criteria
 
A. Termination Criteria for individual subjects:
 
The study will be terminated on individual subjects if any of the following criteria are met:
 
1. Subject requests withdrawal from the study for any reason.2. The clinical study nurses are unable to insert two working Dexcom G6 CGM's prior to beginning the closed loop glucose control session.3. Subject has a Reference Glucose Value less than 54 mg/dL.4. Subject has signs of prolonged severe hyperglycemia, as defined by Reference Glucose Value > 240 mg/dL for more than 2 hours.5. Subject has signs of DKA, as defined by a Reference Glucose Value > 240 mg/dL and blood ketones > 1 mmol/L.6. Subject has signs of HHS, as defined by a Reference Glucose Value > 300 mg/dL for more than 1 hour.7. FUSION system has only one Dexcom G6 CGM available for use for more than 4 hours.8. FUSION system has no Dexcom G6 CGM's available for use for more than 20 minutes.9. There are no Reference Glucose Values for a period of time greater than 60 minutes.10. The FUSION system suffers any unanticipated adverse device effect (UADE).11. The subject has had more than 2% of their estimated total blood volume drawn during visit 3.12. The FUSION system delivers more than 2000 mL (insulin and dextrose infusions) during the 24-hour closed loop glucose control session. 
B. Termination Criteria for the entire study:
 
The entire study will be terminated if the following criteria are met:
 
1. Two subjects experience Reference Glucose Values < 54 mg/dL during the time period the FUSION system is in use.2. Two subjects experience an episode of severe hyperglycemia, as defined by a Reference Glucose Value > 240 mg/dL for more than 2 hours.3. One subject experiences an episode of DKA after starting the closed loop glucose control session.4. One subject experiences an episode of HHS after starting the closed loop glucose control session.5. The FUSION system delivers more than 2000 mL (insulin and dextrose infusions) during the 24-hour closed loop glucose control session in two subjects.6. The FUSION system experiences any unanticipated adverse device effect (UADE).7. The study's principal investigator determines that the safety of the studies subjects is being compromised through use of the FUSION system. |

| | |
|-----|---|

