| 15. | 
Obtain Reference Glucose Values using the Nova StatStrip Hospital Glucose Meter System every 10-60 minutes from time 4 to 32 hours according to the following guidelines:
 
A. Every 10 minutes: Monitor the subject's Reference Glucose Values every 10 minutes whenever either of the following occur:
 
I. Either of the Dexcom G6 CGM's is less than 70 mg/dL.II. When the most recent Reference Glucose Value is less than 70 mg/dL. 
Discontinue every 10 minute Reference Glucose Value monitoring when both of the following have occurred:
 
I. Both Dexcom G6 CGM's are greater than 70 mg/dL.II. The subjects have two consecutive Reference Glucose Values greater than 70 mg/dL. These Reference Glucose Values will be measured by the Nova StatStrip Hospital Glucose Meter System on either a venous or capillary blood sample. 
B. Every 30 minutes: Monitor the subject's Reference Glucose Values every 30 minutes when the following occur:
 
I. After both Dexcom G6 CGM's begin to return glucose readings after their original insertion and prior to the onset of the closed loop glucose control session, for purposes of verifying the accuracy of the CGM's. This monitoring prior to the onset of the closed loop glucose control session may be discontinued once both CGM's have met the following CGM Validation Criteria on two consecutive Reference Glucose Values: 
CGM readings must be within ± 20 mg/dL of the Reference Glucose Value for CGM readings < 100 mg/dL or CGM readings must be within $\pm 20\%$ of Reference Glucose Values for CGM readings ≥ 100 mg/dL on two consecutive Reference Glucose Values.
 
II. During the first 2 hours of the closed loop glucose control session (time 5-7 hours).III. When either Dexcom G6 CGM has a glucose reading less than 85 mg/dL displayed on either the Dexcom G6 Receiver or the Dexcom G6 Follow App.IV. During periods of severe hyperglycemia, which is defined as a CGM or Reference Glucose Value greater than 240 mg/dL.V. When only one Dexcom G6 CGM is available for use by the FUSION system for glucose control.VI. After a CGM has been replaced, and until the replaced CGM has met the above noted CGM Validation Criteria.VII. When the subject experiences any signs of neuroglycopenia, regardless of the glucose level displayed by the CGM's.VIII. From time 29-32 hours, which is the 3 hour time period after conclusion of the closed loop glucose control session. |

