| | 
Both type 1 and type 2 diabetic subjects will consume a lunch consisting of 60 grams of carbohydrates beginning at 1200 hours on day 2.
 
The study nurse will check Reference Glucose Values every 30 minutes with the Nova StatStrip Hospital Glucose Meter System – Times 29, 29.5, 30, 30.5, 31, 31.5, and 32 hours, etc., until the subjects Reference Glucose Values are in the range of 80-250 mg/dL for a period of at least two hours after the completion of the closed loop glucose control session, and the most recent glucose rate of change is less than \pm 2 mg/dL/min.
 
If the subject is removed from the study early due to the presence of hypoglycemia (e.g., < 54 mg/dL or < 70 mg/dL with neuroglycopenic symptoms) or for any other reason, they will have ongoing monitoring in the CRC until they have had glucose values in the range of 80-250 mg/dL for a period of at least two hours, and until their most recent glucose rate of change is less than \pm 2 mg/dL/min. In the event the subject is removed from the study early, any short or long acting insulin dosing needed from the time the subject is removed from the study until the time the subject is discharged from the CRC, will be per the orders of the study's principal investigators ([name] or [name]).
 
If the subjects CGM or Reference Glucose Values are less than 70 mg/dL at the time they are removed from the study, they will have Reference Glucose Values measured every 10 minutes until such time as their glucose values are greater than 70 mg/dL. If the subject develops signs of diabetic ketoacidosis (e.g., Reference Glucose Value > 240 mg/dL and blood ketones > 1 mmol/L), they will have a basic metabolic panel, venous pH, and beta hydroxybutyrate drawn. If the subject develops diabetic ketoacidosis, they will be stabilized and have ongoing care per the usual routine of Emory Healthcare.
 |
| 21. | 
Intravenous Catheter Removal:
 
Remove both IV catheters once the subjects Reference Glucose Value is in the range of 80-250 mg/dL for a period of at least two hours after the completion of the closed loop glucose control session, and when the most recent glucose rate of change is less than \pm 2 mg/dL/min. This criterion will not be met prior to time 32 hours (\sim 1500 hours of 2nd day in the CRC). The subject may be discharged from the CRC unit once this criterion has been met.
 |

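### The rule for ending 10-minute Reference glucose checks after a low is stated inconsistently, and nothing says which version governs a subject removed for hypoglycemia

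*Combined protocol and SAP*

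**What the plan says.** Protocol 2 (IMT2022-1-P2), item 15 sets Reference Glucose Values "every 10-60 minutes from time 4 to 32 hours according to the following guidelines". Part A starts 10-minute checks when either CGM, or the latest Reference value, is below 70 mg/dL. It ends them only when two conditions both hold. The first is "Both Dexcom G6 CGM's are greater than 70 mg/dL" and the second is "The subjects have two consecutive Reference Glucose Values greater than 70 mg/dL".

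A Reference value below 54 mg/dL ends the study for that subject (item 14A, criterion 3: "Subject has a Reference Glucose Value less than 54 mg/dL"; also Section 9.1). Two other places then describe the checks:

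- Section 8.1.1.5 covers subjects removed for a value below 54 mg/dL. Checks are "every 10 minutes, until their Reference Glucose Values are greater than 70 mg/dL". The next step is "They will then have additional Reference Glucose Values drawn every 30 minutes", until values have stayed at 80-250 mg/dL for at least two hours.
- Item 20 (Recovery Period) covers any subject whose CGM or Reference values are below 70 mg/dL at removal: "they will have Reference Glucose Values measured every 10 minutes until such time as their glucose values are greater than 70 mg/dL".

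Section 4.1 has a further version in its list of mitigations. It calls for 10-minute checks if either CGM is below 70 mg/dL or if the most recent Reference value was below 70 mg/dL, and it gives no separate exit rule.

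**The concern.** Item 15A asks for confirmation, by a second Reference value and by both sensors, before checks are spaced out. The removal texts do not repeat the two-consecutive condition, and Section 8.1.1.5 has no CGM condition either. They apply just after a low, when a rescue dose of 50% dextrose may have been given. A single value above 70 mg/dL at that moment could reflect the rescue dose rather than a settled recovery.

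Staff at the bedside would have to decide which text applies. The choice changes the time of the next scheduled Reference check.

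**Working it through.** No sample size, error rate or event count is involved. The check is a comparison of the texts, plus one interval.

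**Step 1. The exit conditions side by side.**

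| Place | Who is covered | Reference condition to leave 10-minute checks | CGM condition | What follows |
|---|---|---|---|---|
| Item 15A | Anyone from time 4 to 32 h with a CGM or latest Reference value below 70 mg/dL | Two consecutive values above 70 | Both above 70 | 30- or 60-minute checks under 15B or 15C |
| Section 8.1.1.5 | Removed for a value below 54 mg/dL | Values above 70; number not stated | None | Every 30 minutes until 80-250 for at least two hours |
| Item 20 | Removed with CGM or Reference values below 70 mg/dL | Glucose values above 70; number and source not stated | Possibly implied | Monitoring until 80-250 for at least two hours, with a rate-of-change limit; the early-removal text gives no interval |
| Section 4.1 | Subjects generally | Latest value no longer below 70 | Neither below 70 | Minimum of every hour |

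**Step 2. Whether the rules meet in one person.** Item 15 runs to time 32 hours, while the closed loop session runs from time 5 to 29 hours, so item 15A is not limited to the session. A subject removed for a value below 54 mg/dL stays in the CRC for monitoring. If that happens before time 32 hours, item 15A and the removal text both apply on their face.

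**Step 3. Whether the plan ranks them.** It does not. Section 10.1 points to the Protocol 2 pages for the frequency of checks, but within a paragraph about the closed loop session. Section 9.2 sends subjects removed for hypoglycemia to the Recovery Period text for monitoring and care. Neither pointer says that one rule displaces the other.

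**Step 4. The next scheduled check after a first Reference value above 70 mg/dL.**

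- Item 15A: a second value is still needed, so the check is due at 10 minutes.
- Section 8.1.1.5, read literally: 10-minute checks can stop at that value, so the check is due at 30 minutes.
- Difference: 30 − 10 = 20 minutes; ratio: 30 / 10 = 3.

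**Step 5. Reach.** A second subject below 54 mg/dL while the system is in use ends the whole study (Section 9.2), and each session's records must be reviewed before the next session (Section 12.1.7). At most about two of the eight subjects could therefore come under the Section 8.1.1.5 text. Item 20 reaches somewhat further, because it covers removal for any reason with a value below 70 mg/dL. The endpoints use data from the period of controller use, so checks after removal do not enter them.

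**The case against.** The strongest reply is that the conflict is one of wording and the patient is protected in other ways. Much of this stands.

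- **Event-driven checks.** Section 4.1 sets CGM alarms below 85 mg/dL and requires a Reference value for any CGM reading below 85 mg/dL or on signs of hypoglycemia. Item 15A restarts whenever either CGM is below 70 mg/dL. Section 10.1 removes the CGMs at the conclusion of the study, and nothing orders earlier removal for a terminated subject. The scheduled interval is therefore not the only check.
- **Ambiguous wording.** The plural in Section 8.1.1.5 could mean more than one value. The sentence in item 20 opens with CGM or Reference values, so its glucose values plausibly include CGM. Neither text says so, and item 15A shows that the plan can state a two-consecutive condition when it wants one.
- **Further safeguards.** Snacks, juice and repeat rescue doses are available, and discharge requires 80-250 mg/dL for at least two hours.

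Three stronger readings are tempting, and the documents do not support them.

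1. A reader might infer that a removed subject is definitely under a weaker rule than one still in the session. Nothing disapplies item 15A, and staff who follow it would also meet the removal texts. What is shown is that the governing rule is unclear.
2. A reader might infer three different check times. Only two can be derived, 10 and 30 minutes, because the early-removal text in item 20 gives no following interval.
3. A reader might infer that a renewed fall below 54 mg/dL would go unseen for up to 30 minutes. From an assumed 75 mg/dL, a fall of (75 − 54)/30 = 0.7 to (75 − 54)/10 = 2.1 mg/dL/min would reach 54 mg/dL between the two scheduled times. But 75 mg/dL is already below the 85 mg/dL alarm, so a CGM reading near the true value would prompt a Reference check first. The inference needs CGMs that are absent or reading high and no prompting symptoms, and the starting value has no source in the plan.

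**Conclusion.** The inconsistency is real. Item 15A and Section 8.1.1.5 give different conditions for leaving 10-minute checks, item 20 leaves the number and source of values open, and no section says which text governs a removed subject who is still in the CRC before time 32 hours. The measurable consequence is a next scheduled check at 10 or at 30 minutes after a first Reference value above 70 mg/dL. The 30-minute figure rests on a literal reading of Section 8.1.1.5.

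The practical risk is limited and arises mainly when the CGMs are unavailable or read falsely high. Section 4.3.2 gives falsely high CGM readings as one reason for taking independent Reference values, so the case is not remote from the plan's own thinking. Few subjects could be affected, and no endpoint or analysis changes. The text is still worth correcting, because it directs bedside monitoring after a severe low.

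**What to change.** Reconcile item 15A, Section 8.1.1.5, item 20 and the Section 4.1 list so that one exit rule for 10-minute checks governs every subject in the CRC, including those removed for hypoglycemia. State the rule once and have the other places cite it. It should say how many values are needed, whether they are Reference or CGM values, what applies if a CGM is not available, and what interval follows. The sponsor's clinicians choose the rule; this review does not propose one.

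The cost is wording. Depending on the rule chosen, an affected subject may need a few extra samples, each a 0.5 mL draw or a fingerstick.

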4.3.4 EXCESSIVE VOLUME LOADING FROM FUSION SYSTEM

In the first in human study performed on two subjects with type 2 diabetes in the CRC, the FUSION system infused an average of 26% of the subject's total daily volume needs during the 24 hour study period. The risks to the subjects from this amount of volume include generalized edema in the setting of abnormal renal/liver function, or exacerbation of underlying congestive heart failure in the setting of underlying congestive heart failure. This risk will be mitigated by selecting subjects who have no underlying renal, liver, or cardiac conditions.

This risk will also be mitigated by further optimizing the FUSION systems glucose control software, based on an analysis of the results from the first two subjects studied. These optimization efforts include steps to prevent excessive use of insulin during states of hyperglycemia (e.g., > 140 mg/dL), which can lead to a rapid fall of elevated glucose values into and through the desired glucose control range of 100-140 mg/dL. This rapid fall of glucose levels leads the FUSION system to either start a dextrose infusion if one is not currently infusing, or to rapidly increase the rate of the current dextrose infusion. The FUSION systems glucose control software will also be optimized to decrease the dextrose infusion more quickly in states where the glucose level is in the desired control range and is either stable or increasing. These efforts to avoid excessive use of dextrose should decrease overall fluid intake, as the dextrose infusion accounted for 88% of the total fluid given by the FUSION system.

Finally, the risk of fluid overload will be minimized through routine monitoring of the subjects for signs of fluid overload, throughout the 24-hour closed loop glucose control session. These signs will include evidence of peripheral edema (swollen hands, ankles, legs, eyelids), increased respiratory rate, shortness of breath, or signs of pulmonary edema on exam such as rales. Excessive volume loading, from the FUSION system, will be defined as fluid delivered by the FUSION system (e.g., insulin infusion and dextrose infusion) in excess of 2000 mL during the 24 hour closed loop session. If this fluid delivery threshold is exceeded on a subject, the study will be stopped on that subject.

The benefits of creating a closed loop glucose control system for use in the inpatient setting outweigh the risks of excessive fluid intake in this highly monitored CRC study.

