If one or both of the Dexcom G6 CGM's are more than 20 mg/dL different from the Reference Glucose Value for CGM values less than 100 mg/dL, or are more than 20% different from the Reference Glucose Value for CGM values greater than or equal to 100 mg/dL at any time during visit 3, they will be recalibrated against the result from the Reference Glucose Value (using the Dexcom G6 receiver(s)). This calibration must occur within 5 minutes of obtaining the Reference Glucose Value sample. If the Dexcom G6 Receivers are recalibrated, the matching mobile phone's Dexcom App must also be recalibrated at the same time (e.g., if Dexcom Receiver #1 is recalibrated, also recalibrate the Dexcom G6 Follow App in mobile phone #1). If a Dexcom G6 sensor is recalibrated, a follow up CGM one hour after the recalibration must be within 20 mg/dL of the Reference Glucose Value for CGM values less than 100 mg/dL, or within \pm 20% of the Reference Glucose Value for CGM values greater than or equal to 100 mg/dL. If a CGM is felt to be inaccurate – cannot be calibrated to meet the aforementioned CGM Validation Criteria – it may be replaced according to the CGM Replacement Criteria.
2. The Dexcom G6 CGM's are greater than 20% different than their averaged value. If the averaged glucose value of the two Dexcom G6 CGM's is greater than 20% different than the CGM values, a Reference Glucose Value will be obtained and both CGM's will be re-calibrated against the result of the Reference Glucose Value using the Dexcom G6 receivers. This recalibration must occur within 5 minutes of obtaining the Reference Glucose Value sample. In this scenario, the FUSION system will automatically alert the clinical study staff of the need to recalibrate both Dexcom G6 CGM's. If the Dexcom G6 Receivers are recalibrated, the matching mobile phone's Dexcom Follow Apps must also be recalibrated at the same time. If a Dexcom G6 CGM is recalibrated, the CGM value one hour after recalibration must be within 20 mg/dL of the Reference Glucose Value for CGM values less than 100 mg/dL, or within \pm 20% of the Reference Glucose Value for CGM values greater than or equal to 100 mg/dL.

DEMONSTRATION OF AN ARTIFICIAL INTELLIGENCE BASED CLOSED LOOP GLUCOSE CONTROL SYSTEM AS A THERAPEUTIC MODALITY IN TYPE 1 AND TYPE 2 DIABETIC PATIENTS

Protocol IMT 2022-1

CONFIDENTIAL

Version1.0.7

22 August 2022

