|-----|---|

| | |
|-----|--|
| | 
C. Every 60 minutes: Monitor the subject's Reference Glucose Value every 60 minutes when the following occur:
 
During the last 22 hours of the closed loop glucose control session (time 7-29 hours), if the following occur:
Both CGM's are in the range of 85-240 mg/dL and the subject is not experiencing any signs of neuroglycopenia. 
Result: _____ mg/dL, Time: _____ (24 hour clock) Note: Notify study team if the CGM or Reference Glucose Value is < 70 mg/dL or > 300 mg/dL.
 |
| 16. | 
Dexcom G6 CGM Placement, Calibration and Replacement
 
Visit 3 (Time 0 to 5 hours): Place two Dexcom G6 CGM's in the abdomen 5 cm to the right and left of the umbilicus (Figure 28).
  
18 years and older
 
Figure 28 – Green shaded areas denote appropriate areas of the abdominal wall to place the Dexcom G6 CGM's. This figure is from the Dexcom G6 CGM user manual.
 |

Make sure the Dexcom G6 Transmitters are labeled “#1” and “#2”. These labels should be in a clearly visible position after the Transmitters have been attached to the Dexcom G6 glucose sensors. Once both Dexcom CGM’s begin to return glucose values, obtain a Reference Glucose Value using the Nova StatStrip Hospital Glucose Meter System. If either of the Dexcom CGM’s do not meet CGM Validation Criteria, they may be calibrated. The Dexcom G6 CGM’s must meet the following CGM Validation Criteria throughout the CRC study session (visit 3), otherwise they will be calibrated as often as is necessary:

1. CGM readings must be within ± 20 mg/dL of the Reference Glucose Value for CGM readings < 100 mg/dL or CGM readings must be within $\pm 20\%$ of Reference Glucose Values for CGM readings ≥ 100 mg/dL on two consecutive Reference Glucose Values.

Calibrations should only be attempted when the glucose rate of change is less than ± 2 mg/dL/min on the Dexcom G6 CGM (see figure 29).

If after two calibration attempts prior to beginning the closed loop glucose control session (time 0-5 hours) the CGM(s) still do not meet CGM Validation Criteria, they may be replaced. The closed loop glucose control session may not begin until there are two working Dexcom G6 CGM’s in place, and both CGM’s have met the above noted CGM Validation Criteria.

Closed Loop Glucose Control Session (Time 5 to 29 hours):

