Inspect the CGM sites (see Monitoring Activities) and ensure proper performance and communication to the two Dexcom G6 Receivers that are labeled “#1” and “#2”, and that are part of the FUSION system (Figure 20); ensure communication with the Dexcom G6 Follow APP on the two mobile phones labeled “#1” and “#2”. The CGM’s may be replaced during the closed loop glucose control session for any of the following reasons:

1. The CGM(s) do not meet the above noted CGM Validation Criteria and are unable to be calibrated after two attempts over a two-hour period of time.
2. If the CGM measurement is > 180 mg/dL and the simultaneous (e.g., within 5 minutes) Reference Glucose Value is < 100 mg/dL, the CGM may be replaced as this scenario may lead to inadvertent insulin administration by the FUSION system, which may result in hypoglycemia (< 70 mg/dL).
3. If the CGM measurement is < 100 mg/dL and the simultaneous (e.g., within 5 minutes) Reference Glucose Value is > 180 mg/dL, the CGM may be replaced as this scenario may lead to a delay in the treatment of hyperglycemia, which will increase the risk for DKA in type 1 diabetic subjects.

Trend Arrow: Steady

Changing:

- Less than 1 mg/dL each minute
- Up to 15 mg/dL in 15 minutes

Trend Arrow: Slowly Rising or Falling

Changing:

- 1 – 2 mg/dL each minute
- Up to 30 mg/dL in 15 minutes

Figure 29 – Glucose rate of change, as noted by the Dexcom G6 CGM trend arrows.

| | |
|-----|---|

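### In hours 7-29 a CGM in use that has just failed validation stays on 60-minute Reference checks, while a replacement CGM not yet validated gets 30-minute checks

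*Combined protocol and SAP*

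**What the plan says.** Protocol 2 (IMT2022-1-P2), item 15, sets the Reference schedule.

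- **Item 15C, every 60 minutes.** In hours 7-29 this applies when both CGMs "are in the range of 85-240 mg/dL and the subject is not experiencing any signs of neuroglycopenia".
- **Item 15B, every 30 minutes.** Trigger VI reads "After a CGM has been replaced, and until the replaced CGM has met the above noted" criteria. Trigger I also covers unvalidated CGMs, but only before the loop starts: "This monitoring prior to the onset of the closed loop glucose control session may be discontinued once both" CGMs have passed on two consecutive References. Other triggers include a CGM below 85 mg/dL, a CGM or Reference above 240 mg/dL, only one CGM available, and neuroglycopenia.
- **Item 15A, every 10 minutes.** This applies when a CGM or the last Reference is below 70 mg/dL.

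For a CGM that fails validation, Section 8.1.1.4 requires recalibration: "This calibration must occur within 5 minutes of obtaining the Reference Glucose Value sample". It continues: "If a Dexcom G6 sensor is recalibrated, a follow up CGM one hour after the recalibration must be within 20 mg/dL" of the Reference, or within 20% at CGM values of 100 mg/dL or more. Item 16 adds that CGMs are to be calibrated as often as needed throughout visit 3, but also limits when: "Calibrations should only be attempted when the glucose rate of change is less than" ±2 mg/dL/min. Item 16 permits replacement during the loop for CGMs that fail validation and "are unable to be calibrated after two attempts over a two-hour period of time", and sooner for gross discrepancies.

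Section 4.3.1 states that the controller acts on the simple average of the two CGMs. Sections 5 and 11.1 compute the endpoints from those control data unless otherwise specified.

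**The concern.** A replacement CGM awaiting validation and a CGM in use that has just failed are both unconfirmed. The second has also been shown to be wrong, yet it stays on the looser schedule. Sixty minutes is the longest interval allowed, since Section 9.1 criterion 9 terminates the subject when there is no Reference for more than 60 minutes.

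The 60-minute rule also relies on the CGM readings themselves. Section 4.3.2 says that References exist to catch hypoglycemia when CGMs feed falsely high values to the controller. Under item 15C, a falsely high CGM helps to keep the subject on hourly checks.

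What is at stake is the time for which an autonomous intravenous insulin controller may act on an average containing a wrong reading before a re-check falls due. Because the endpoints use the same data, true glucose below 70 mg/dL could also be scored as 70-180 mg/dL in that time.

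**Working it through.** **1. Which failures stay on 60 minutes.** Items 15A-15C and the validation criteria were applied to pairs of values in whole mg/dL, with two CGMs reading the same and no neuroglycopenia. These Reference values fail validation but leave the interval at 60 minutes:

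| Both CGMs | Reference too low | Reference too high |
|---|---|---|
| 100 | 70-83 | 126-240 |
| 140 | 70-116 | 176-240 |
| 180 | 70-149 | 226-240 |
| 240 | 70-199 | none |

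For example, CGMs at 180 with Reference 100 are 80% high. The interval is 60 minutes for sensors already in use and 30 minutes if one is an unvalidated replacement. Item 16's immediate-replacement option does not apply, because it needs a CGM above 180 and a Reference below 100. Where it does apply and is used, 15B VI takes over.

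**2. What recalibration changes.** If it holds, later readings are right and nothing after it is mis-scored. At Reference 70-84, a correction that holds also brings the CGM below 85 and so onto 30-minute checks. Two cases remain: the correction does not hold, or it is delayed because glucose is changing by 2 mg/dL/min or more.

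**3. Whether the discrepancy alarm helps.** It fires when a CGM is more than 20% from the average. For readings a > b, (a − b)/(a + b) > 0.20 means a/b > 1.5. Errors in the same direction can pass unnoticed.

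**4. Length of the wait.** Assume one control value per 5 minutes: 24 × 60/5 = 288 per session.

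- Hourly: 60/5 = 12 values; 12/288 = 4.2%.
- Half-hourly: 30/5 = 6 values; 6/288 = 2.1%.
- Two attempts over two hours: 120/5 = 24 values; 24/288 = 8.3%, with 120/60 = 2 scheduled References instead of 120/30 = 4.

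The percentages are the same with one value per 10 minutes.

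**5. When glucose below 70 would be hidden without a CGM trigger.** Both CGMs must read at least 85 while true glucose is at most 69. The lower CGM must then be at least 85 − 69 = 16 mg/dL, or 85/69 = 1.23 times, too high. As an illustration with assumed values, take Reference 90 and CGMs 130 and 115. Both fail (130/90 = 1.44; 115/90 = 1.28). The average is 122.5, and each CGM is 7.5/122.5 = 6.1% from it, so there is no alarm. If recalibration fails or lapses:

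- Proportional error: the lower CGM reaches 85 at true glucose 85/1.278 = 66.5, so 67-69 is hidden.
- Fixed offsets of +40 and +25: the lower CGM reaches 85 at true glucose 60, so 60-69 is hidden.

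**6. Rapid falls.** At 2 mg/dL/min a CGM starting at 140 reaches 85 in (140 − 85)/2 = 27.5 minutes, and one starting at 180 in 47.5 minutes. A continuous fall lasts a full hour without that trigger only from 85 + 2 × 60 = 205 or more.

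**The case against.** The strongest reply is that the protocol does not leave a failed CGM alone. Section 8.1.1.4 requires recalibration whenever a CGM fails during visit 3, and item 16 requires it as often as needed. Each attempt needs a Reference no more than 5 minutes old. A reader of item 15 alone might infer that no Reference is due before the next hourly one. The documents do not support that: this is a continuing duty that implies extra References. What survives is that they are untimed. A correction that has not held may show only against a further Reference, and the only stated time for that is one hour.

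Section 4.3.4 describes excess insulin "which can lead to a rapid fall of elevated glucose values into and through the desired glucose control range of 100-140 mg/dL", which makes delayed calibration look like the main danger. The arithmetic above limits this: a fast fall through the control range soon brings a CGM below 85, and Section 4.1 item 4 and 15B III then apply.

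Two further points stand. Trigger 15B I applies only before the session, so the fair comparison in hours 7-29 is with a replaced CGM alone. A CGM in use has also passed validation before the loop, which a replacement has not. That justifies trust until it fails, but is weaker afterwards.

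Section 4.1 makes hourly sampling a minimum, so staff may check sooner, but no line sets an earlier time. Section 10.1 mentions 30-minute sampling on initiation, then refers to the schedule in item 15, so it does not close the gap.

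**Conclusion.** The gap is real but modest. It applies in hours 7-29 with two CGMs at 85-240 mg/dL, the last Reference at 70-240 mg/dL and no neuroglycopenia. There, a CGM known to have failed can stay in the control average for up to 60 minutes before a timed re-check, against 30 minutes for an unvalidated replacement. It matters only when recalibration does not hold or is delayed.

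A reader might take 4.2% or 8.3% as bias in the primary endpoints. They are ceilings on waiting time per event, under an assumed 5-minute control interval. The documents give no rate of failed checks or failed recalibrations, so no expected bias follows. An earlier Reference shortens the wait but does not itself change a CGM value already recorded, or permit calibration while glucose is moving too fast.

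Hourly References, symptom-triggered checks, the below-85 trigger and the stop at a Reference below 54 mg/dL all remain. The change is still worth making, because it applies the protocol's own 30-minute standard at little cost.

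**What to change.** 1. Add a trigger to item 15B: *a CGM in use has failed the CGM Validation Criteria, until it passes on two consecutive References*. The two-pass form matches items 15B I and 16.
2. Make item 15C conditional on both CGMs currently meeting the criteria.
3. In Section 8.1.1.4, change the follow-up after recalibration from one hour to 30 minutes, in both calibration scenarios. Otherwise it would conflict with the new trigger.

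**Cost.** One extra 0.5 mL draw per hour in failed status. The ceiling, with a CGM failing for all 22 hours, is 22 draws or 11 mL. Scheduled draws from hour 4 to 32 rise from 7 + 22 + 6 = 35 (17.5 mL) to 7 + 44 + 6 = 57 (28.5 mL). That is within the 60 or so draws and 40 mL in Section 10.1 item 6. With the 10 mL screening draw it is 38.5 mL, under the 80 mL total. Extra References for recalibration or low glucose come on top, as they do now. The 100 syringes and 100 strips listed in Protocol 1 suffice for the scheduled draws.

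A descriptive sensitivity analysis that flags control values around failed checks is optional and not needed for this fix.
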